**Table 1. Variables**

Variable	CRF Booklet 01	CRF Booklet 02
Written consent to participate in this study	●*	
Characteristics of subjects	○	
Subject ID	○	
Gender	○	
Date of birth	○	
Record of vaccination with this product	○	
Clinical history (concurrent illness/past history)	○	
Allegy information	○	
Suspected pregnancy/Lactation (women only)	○	
Current medications	○	
Pregnancy and lactation (woman only)	↔	↔
Information on inoculation of vaccines	↔	↔
Information on COVID-19 pathogen test	↔	↔
Information on COVID-19	↔	↔
Serious adverse events	↔	↔
End-of-study discontinuation record (reason)	●	●

\* : Identify subjects consented to participate in this study.

○: For patients consented to participate in this study, the data collected in the Investigation of Health Status of Recipients Vaccinated First will be replicated and stored in the database for this study.

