4. HYPOTHESES AND DECISION RULES

Because of the non-confirmatory nature of this study, no hypothesis tests will be performed in this study.

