5.4. Subgroups

Subgroup analyses of safety will be performed with respect to the following recipient characteristics (factors). The subgroups in each categorization are indicated in the squared brackets [] with the reference for risk ratio/difference being underlined.

- Sex [male, female]

- Age [<55 yrs., ≥55 yrs.], [<65 yrs., ≥65 yrs.]
- Past history of allergy [absent, present]

In addition, subgroup analyses of safety with respect to other factors indicated below will be performed, as necessary:

- Suspected pregnancy/Lactation (women only, for each dose number for initial immunization) [absent, present]
- Pregnancy (women only) [absent, present]
- Lactation (women only) [absent, present]
- History of other vaccination (except boosts) [absent, present]
- Renal impairment [absent, present]
- Hepatic impairment [absent, present]

Presence/absence of renal/hepatic impairment should be determined according to “Attachment: Procedure to Extract Patients with Hepatic/Renal Impairment in Post-Marketing Investigations”.

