9.1.3. Binary variables

For binary variables, subjects included in each binary category will be calculated in terms of frequency and proportion. When a confidence interval (CI) is determined for a proportion, the two-sided 95% CI (exact method) will be determined.

When a comparison for proportion is made between subgroups, the risk ratio and its 95% CI will be calculated. They will also be presented graphically (See Appendix 1).

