9.2.2. Subject characteristics and treatment history

9.2.2.1. Subject characteristics

Using the safety analysis set, characteristics of vaccinated subjects collected in the Investigation of Health Status of Recipients Vaccinated First will be summarized according to Section 8.1, with respect to the following factors:

- Sex [male, female]
- Age (continuous)

- Age (categorical) [≥ 0 to <10 yrs., ≥ 10 to <20 yrs., ≥ 20 to <30 yrs., ≥ 30 to <40 yrs., ≥ 40 to <50 yrs., ≥ 50 to <60 yrs., ≥ 60 to <70 yrs., ≥ 70 to <80 yrs., ≥ 80 to <90 yrs., ≥ 90 yrs.]
- Past history [absent, present]
- Complications [absent, present]
- Allergy [absent, present]
- Suspected pregnancy/Lactation (women only, for each dose number for initial immunization) [absent, present]
- Pregnancy (women only) [absent, present]
- Lactation (women only) [absent, present]
- Duration of safety assessment (days)
- Number of doses for initial immunization during the study period for the Investigation of Health Status of Recipients Vaccinated First [1 dose, 2 doses]
- Dose interval for initial immunization (recipients of two doses only) (day of 2nd dose – day of 1st dose)
- Booster (third) vaccination [absent, present (this product, other), unknown]

Using the safety analysis set, a breakdown of subjects according to each of the following factors will be presented in terms of n and proportion by system organ class (SOC) and preferred term (PT):

- Past history
- Complications

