9.2.3.4. Subgroup analyses

Subjects with at least one serious adverse reaction will be summarized in terms of n and proportion by each factor defined in Section 5.4. According to Section 9.1.3, risk ratios between subgroups will be determined and graphically presented for the proportion of subjects with any serious adverse reactions. For all factors except sex and age, risk ratios adjusted for sex and age (<65 yrs., ≥65 yrs.) will also be determined using the Mantel-Haenszel method, and graphically presented. If there is a category with only <5 subjects and recategorization has been determined to be infeasible after consideration, however, the risk ratio for such category may not be determined.

For each of the following factors among specified in Section 5.4, subjects who had serious adverse reactions will be summarized by SOC and PT in terms of n and proportion.

- Age [<65 yrs., ≥65 yrs.]
- Pregnancy (women only) [absent, present]
- Renal impairment [absent, present]
- Hepatic impairment [absent, present]

Serious adverse events will also be analyzed in the same manner.

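### SAP 9.2.3.4 plans only crude risk ratios for sex and age, so the two may confound each other; a mutually adjusted ratio for each would cost a few table rows (minor).

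*SAP*

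**What the plan says.** SAP 5.4 fixes three subgroup factors: sex, age and past history of allergy. Age enters as two dichotomies: "Age [<55 yrs., ≥55 yrs.], [<65 yrs., ≥65 yrs". The remaining factors (pregnancy, lactation, other vaccination, renal and hepatic impairment) are analysed only as necessary.

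For the measure, SAP 9.1.3 states: "When a comparison for proportion is made between subgroups, the risk ratio and its 95% CI will be calculated". SAP 9.2.3.4 applies this to the proportion of subjects with any serious adverse reaction, by each factor. It then adds adjusted ratios: "For all factors except sex and age, risk ratios adjusted for sex and age (<65 yrs., ≥65 yrs.) will also be determined". The method is Mantel-Haenszel, and these ratios are graphed too. Serious adverse events are handled in the same way.

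The material for a mutual adjustment is already in the plan. Protocol Table 1 lists gender and date of birth among the items for which, in consenting subjects, "the data collected in the Investigation of Health Status of Recipients Vaccinated First will be replicated and stored in the database for this study". SAP 9.2.2.1 already derives 10-year age bands, beginning "Age (categorical) [≥ 0 to <10 yrs., ≥ 10 to <20 yrs".

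On status, SAP 4 states that "no hypothesis tests will be performed in this study". SAP 6.4 identifies no covariates.

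**The concern.** Of the three fixed subgroup factors, only allergy history receives an adjusted ratio. Sex and age are shown crude only, on the same kind of graph as the adjusted ratios for the other factors, and nothing says that they are not independent effects.

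The revision history shows that the sex- and age-adjusted ratios were added in SAP version 4.0. That addition makes sense only if sex and age are thought capable of distorting a comparison of event risk. If so, each could distort the other wherever the age distribution differs between men and women. A crude male:female ratio could then partly reflect age, and a crude older:younger ratio could partly reflect sex. A reader of the safety report might take either as an effect of the factor itself.

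**Working it through.** **1. What the planned ratio is.** Appendix 1 of the SAP is a template, not data, but it shows the calculation. For sex, 18/2220 against 3/1099:

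- RR = (18/2220)/(3/1099) = 2.970.
- SE(log RR) = √(1/18 − 1/2220 + 1/3 − 1/1099) = 0.6225.
- 95% CI = 2.970 ×/÷ exp(1.96 × 0.6225) = 0.877 to 10.062. The SAP prints 2.97 (0.88–10.06).

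The template age row gives 1.809 (0.423–7.745) against the printed 1.81 (0.42–7.74). Both rows are ordinary crude ratios.

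**2. Inputs for the size of a possible shift.** The documents give no sex-by-age table and no event rates. Everything below is assumed, except the maximum of 20,000 subjects (protocol 8.5.1).

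- Men 35%, so 7,000 men and 13,000 women.
- Age shares in the 20s, 30s, 40s, 50s and 60+: women 25/25/27/18/5%. Men (a) 20/26/26/18/10%, (b) 15/25/25/22/13%, (c) 12/22/24/24/18%.
- Risk of a serious adverse event in band k = 0 to 4: r_k = 0.2% × g^k, the same for both sexes, with g = 1.3, 1.5 or 2.0.
- For a cut at 65, 40% of the 60+ band is taken as 65 or older.

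**3. Formulas.** Crude RR = Σ m_k r_k / Σ f_k r_k, where m_k and f_k are the male and female age shares. Mantel-Haenszel RR = Σ(a_k n0_k/N_k) / Σ(b_k n1_k/N_k) on expected counts, where a_k and b_k are male and female events, n1_k and n0_k are male and female subjects, and N_k is the stratum total.

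**4. Middle case, mix (b), g = 1.5.** The band risks are 0.2, 0.3, 0.45, 0.675 and 1.0125%.

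- Men: 0.0300 + 0.0750 + 0.1125 + 0.1485 + 0.1316 = 0.4976%.
- Women: 0.0500 + 0.0750 + 0.1215 + 0.1215 + 0.0506 = 0.4186%.
- Crude RR = 0.4976/0.4186 = 1.19, although the true sex ratio is 1.00.
- Expected events are 34.8 in men and 54.4 in women, so SE = 0.2165 and the 95% CI is 0.78 to 1.82.

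**5. All nine combinations.**

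| Male mix | g | Crude RR (95% CI at 20,000) | MH, cut at 65 |
|---|---|---|---|
| a | 1.3 | 1.06 (0.64–1.76) | 1.04 |
| a | 1.5 | 1.09 (0.71–1.69) | 1.06 |
| a | 2.0 | 1.18 (0.87–1.60) | 1.12 |
| b | 1.3 | 1.12 (0.68–1.84) | 1.09 |
| b | 1.5 | 1.19 (0.78–1.82) | 1.14 |
| b | 2.0 | 1.35 (1.01–1.81) | 1.25 |
| c | 1.3 | 1.18 (0.72–1.93) | 1.14 |
| c | 1.5 | 1.30 (0.86–1.96) | 1.22 |
| c | 2.0 | 1.55 (1.17–2.06) | 1.39 |

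Mantel-Haenszel over the five bands returns 1.00 in every row. It must, because risk was set constant within a band. In seven of the nine rows the crude interval includes 1; the two exceptions need risk to double per decade.

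**6. Null cases.** With equal age mixes, or with g = 1, the crude ratio is 1.00.

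**7. Check with a simpler model.** With one age cut and age risk ratio R, the sex ratio is multiplied by [1 + p_m(R−1)]/[1 + p_f(R−1)], where p_m and p_f are the male and female shares aged 65 or older. With 10% and 3%, R = 2, 3 and 5 give 1.07, 1.13 and 1.25. With 20% and 5% they give 1.14, 1.27 and 1.50. With 5% in both sexes the factor is 1.00.

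**8. Age ratios.** The illustration in steps 2 to 5 assumes no sex effect, so sex cannot confound the age ratios in it and it yields no size for them. It also models serious adverse events of any cause, and nothing in it speaks to an age gradient in serious adverse reactions.

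**The case against.** The best defence is that these are descriptive ratios, and that the exemption only stops the two adjusters being adjusted for themselves. There are no tests and no decision rule. Protocol 8.9 already names confounding and the missing control group as limitations, and SAP 9.2.3.5 allows further analyses. A crude sex or age ratio is a correct description of who had events.

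Much of this stands. No endpoint, analysis set or decision depends on these ratios. Three parts do not carry the point away:

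- Not adjusting sex for sex does not explain leaving sex unadjusted for age, or age unadjusted for sex.
- Protocol 8.9 ascribes unaddressed confounding to insufficient background information, whereas here both variables are copied for consenting subjects.
- SAP 9.2.3.5 reports exploratory results only when they give an important interpretation, so reporting would depend on the result.

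A reader might infer something stronger: that the sex ratio is confounded by age and the age ratios by sex, as a fact. The documents do not support that. They show neither a sex-age association in this cohort nor a relation of either variable to the event, and without one of these links the factor is exactly 1.00. The illustration cannot fill the gap, because every male mix in it was assumed to have more subjects aged 60+ than the female mix. With younger men the shift would run the other way.

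**Conclusion.** The gap in the text is certain: sex and age ratios are planned crude only. That they may be mutually confounded is a possibility, conditional on two links on which the documents give no figures.

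For the sex ratio on serious adverse events, an assumed older male workforce and risk rising 1.3- to 2-fold per decade would give a crude ratio of 1.06 to 1.55 with no true sex effect. The upper end needs the oldest male mix and risk doubling per decade. At the protocol maximum of 20,000 subjects most of these shifts are within sampling error. That limits their importance but does not justify leaving in a bias that can be removed, since the confidence interval does not allow for it. No size is claimed for the age ratios or for serious adverse reactions.

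This is a minor reporting improvement, worth making because it needs no new data.

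**What to change.** Amend the adjustment sentence in SAP 9.2.3.4 so that, for both serious adverse reactions and serious adverse events:

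- the sex ratio is also given Mantel-Haenszel adjusted for age in the 10-year bands of SAP 9.2.2.1;
- each age ratio (cuts at 55 and at 65) is also given Mantel-Haenszel adjusted for sex;
- crude and adjusted ratios stand side by side and are described as descriptive.

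Deleting the exemption alone would not be enough for sex. It would adjust sex by the single cut at 65, which in the illustration still leaves 1.04 to 1.39.

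The cost is SAP wording, three extra rows per endpoint, and slightly wider intervals where strata are sparse. No data collection changes. SAP version 6.0 carries the status that all data are fixed, so the added ratios should be labelled as specified after that point.

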### 8.3.1. Characteristics of subjects

Enter the presence or absence of written consent for participation in this study.

Identify subjects from whom written consent was obtained through entry, and the following data of relevant subjects collected in the Investigation of Health Status of Recipients Vaccinated First will be replicated and stored in the database for this study.

Such information will be used as subject characteristics for this study.

- Subject ID
- Gender
- Date of birth
- Record of vaccination with this product (date of vaccination/name of vaccine/lot number/side of vaccination)
- Clinical history (concurrent illness and past history)
- Allergy information (information on presence/absence of allergy and allergen)
- History of other vaccinations (within 1 month after the first or second vaccination with this product)
- Suspected pregnancy/Lactation (women only)
- Current medications (names of drugs concomitantly used at the time of 1st or 2nd vaccination)

PFIZER CONFIDENTIAL

---

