#### **8.9. Limitations of the research methods**

There may be potential limitations in this study:

1. Since no control group is included in the study, there is a limitation in determining whether or not a risk of developing adverse events and adverse reactions increases with inoculation of this product.
2. Due consideration may not be given to confounding factors due to insufficient background information collected.
3. Since this study collects the information from medical interview based on health status record forms and records such as medical records, specified data may not be collected or may be missing.

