6.4. Covariates

No covariates or potential covariates have been identified for the safety or effectiveness of this product on the basis of currently available data including those from clinical studies.

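### For pregnancy and lactation, the risk ratio described as adjusted for sex and age has no age adjustment among women under 65, where the exposed women are expected to lie

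*SAP*

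**What the plan says.** SAP 9.2.3.4 has crude risk ratios between subgroups presented graphically. For every factor other than those two demographic ones, sex and age, it plans a second set of ratios: "risk ratios adjusted for sex and age (<65 yrs., ≥65 yrs.) will also be determined using the Mantel-Haenszel method". These are plotted as well. The rule is first given for serious adverse reactions and then extended: "Serious adverse events will also be analyzed in the same manner".

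The factors come from SAP 5.4. Among those to be analysed if judged necessary is "Suspected pregnancy/Lactation (women only, for each dose number for initial immunization) [absent, present", followed by pregnancy and lactation, each also restricted to women. No exception, other age cut or other adjustment is given for these three.

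Finer age groups exist elsewhere in the SAP. Section 9.2.2.1 describes subjects in 10-year bands, including "≥ 20 to <30 yrs., ≥ 30 to <40 yrs., ≥ 40 to <50 yrs". Date of birth is among the items that Protocol 8.3.1 copies from the earlier investigation: "Such information will be used as subject characteristics for this study".

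**The concern.** Pregnancy and lactation are closely tied to age, so the exposed women sit in a narrow range, while the comparators run across the working ages of healthcare staff. An age cut at 65 does not separate these groups where it matters. A reader who sees a crude ratio beside one described as adjusted for sex and age will conclude that age has been dealt with. Here the second ratio only removes comparators aged 65 or over. The two values can differ, which makes the second look like the product of real age control.

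Safety in pregnant or nursing women is the missing information named in SAP 2.3.2, and the final analysis supports the re-examination application (SAP 3). If the risk of serious events rises with age, the uncorrected comparison leans towards false reassurance.

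**Working it through.** **Check of the crude formula.** The documents give no result for these factors. The mock-up in SAP Appendix 1 allows a check of the basic ratio: (18/2220)/(3/1099) = 2.97, with a log-scale Wald 95% interval of 0.88 to 10.06, as printed. All nine mock-up ratios agree to rounding.

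**The identity.** In stratum i, let a and c be events among n1 exposed and n0 comparators, with N = n1 + n0. Then

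RR_MH = Σ(a·n0/N) / Σ(c·n1/N).

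- Sex is constant for a women-only factor. If men were coded as absent, their strata would have n1 = 0 and drop out.
- If no exposed woman is 65 or older, that stratum has a = 0 and n1 = 0 and adds zero to both sums.
- One stratum remains: RR_MH = (a/n1)/(c/n0) in women under 65. The Greenland-Robins variance reduces to 1/a − 1/n1 + 1/c − 1/n0, so the confidence interval is the same too.

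In 20,000 random tables the ratio and the variance matched exactly every time.

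**Worked example (assumed counts).** Exposed under 65: 1/225. Comparators under 65: 40/12,350. Comparators 65 or over: 5/650.

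- Planned: (1 × 12,350/12,575)/(40 × 225/12,575) = 1.372.
- Crude under 65: (1/225)/(40/12,350) = 1.372.
- Crude, all women: (1/225)/(45/13,000) = 1.284.

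**Sensitivity to the proviso.** The documents give no count of exposed women aged 65 or over. In a second example (exposed 3/200, comparators 60/11,000 under 65 and 20/800 at 65 or over) the planned ratio is 2.75 with none. With 1, 3 or 10 such women it becomes 2.69, 2.57 or 2.23 if none has an event, and 3.60, 3.44 or 2.98 if one does. The identity also assumes no continuity correction; adding 0.5 to the cells of the empty stratum gives 3.14.

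**Number of ratios.** Two dose-specific suspected pregnancy/lactation, one pregnancy and one lactation, each for reactions and events: (2 + 1 + 1) × 2 = 8.

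**Possible bias (all inputs assumed).** True ratio 1; risk multiplies by g per decade; exposed women 40/57/3% in their 20s/30s/40s; comparators under 65 spread evenly over 20 to 64. For g = 2, the mean relative risk is 0.40 + 0.57×2 + 0.03×4 = 1.66 in the exposed and [10(1+2+4+8) + 5×16]/45 = 5.11 in comparators, a ratio of 0.32.

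| g per decade | 0.8 | 1.0 | 1.2 | 1.5 | 2.0 |
|---|---|---|---|---|---|
| Planned, even mix | 1.25 | 1.00 | 0.79 | 0.56 | 0.32 |
| Planned, younger comparators | 1.10 | 1.00 | 0.89 | 0.73 | 0.52 |
| Planned, older comparators | 1.32 | 1.00 | 0.76 | 0.52 | 0.29 |

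With 10-year bands the ratio is 1.00 if risk steps by decade and 0.96 to 1.00 if it changes continuously.

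**Precision (assumed 13,000 comparators).** With 225 exposed and 0.3% risk in the 20s, 0.59 to 1.12 exposed events are expected over g = 0.8 to 2.0, with a 55% to 33% chance of none. The SE of the log ratio (even mix) runs from 1.314 to 0.945, so the 95% limits lie about 13-fold to 6-fold either side. With 1,000 exposed: 2.6 to 5.0 events and limits 3.6-fold to 2.4-fold. At 0.03% risk and 225 exposed, as might apply to serious reactions, 0.06 to 0.11 events are expected and 89% to 94% of data sets have none.

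**The case against.** The SAP does what it says: the two age strata are named in the same sentence as the adjustment, and dropping comparators aged 65 or over is a real and correct effect. What remains is residual confounding within a broad band, which any dichotomised age adjustment leaves. The same cut is used for allergy history, other vaccination and renal and hepatic impairment, so changing it for three factors gives the section two rules. No bias is shown from the documents: SAP 6.4 states that "No covariates or potential covariates have been identified for the safety or effectiveness of this product", and every rate, age mix and exposed count above is assumed. With 225 exposed women at 0.3% risk, the modelled bias exceeds one SE only when risk doubles per decade, and then not with younger comparators. The output is descriptive (SAP 4 excludes hypothesis tests), is run only as needed, and sits beside tabulations and listings of pregnant subjects where rare events would be read. SAP 9.2.3.5 already permits extra analyses, and Protocol 8.9 already warns: "Due consideration may not be given to confounding factors due to insufficient background information collected".

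Much of this stands, and it keeps the stakes low. It does not remove the point. For the other factors, exposed subjects can fall on both sides of 65, so the adjustment can work across strata; here it cannot. The Protocol 8.9 warning concerns information not collected, whereas date of birth is held. Permission for an additional analysis does not correct the description of the planned one. A wide interval shows imprecision to the reader; nothing in the output shows that the age adjustment is missing.

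**Conclusion.** The point holds. Provided no exposed woman is 65 or older, and with the standard estimator, the sex- and age-adjusted ratio for each women-only factor is the crude ratio in women under 65. The proviso is plausible for pregnancy and lactation, but the documents do not confirm it.

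Whether this biases the ratio depends on the age mix and the age gradient of risk, neither of which the documents give. Over the assumed range the planned ratio averages from 1.32 to 0.29 when the truth is 1, and it is unbiased if risk is flat. At 225 exposed women the 95% limits are wider than the bias throughout. With 1,000 exposed and risk doubling per decade, the bias is 1.4 to 2.7 SE. Serious-reaction ratios will usually be uninformative under either rule. This is a worthwhile, inexpensive improvement to a descriptive analysis; it does not threaten the study's main tabulations. It does not extend to renal impairment, hepatic impairment or the other factors.

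**What to change.** First confirm from the data that no exposed woman is 65 or older. Then add to SAP 9.2.3.4:

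*For the women-only factors in Section 5.4, Mantel-Haenszel risk ratios will be stratified by the 10-year age bands of Section 9.2.2.1; bands with no exposed women contribute nothing and are not merged. The rule on fewer than 5 subjects applies to the factor categories, not to the age bands. A ratio with a zero denominator is shown as not estimable.*

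The second sentence is needed because the present wording, "If there is a category with only <5 subjects and recategorization has been determined to be infeasible after consideration", could be read as covering age bands. Show the ratio under the present rule alongside, labelled *women <65 years, no age adjustment within this group*. Record that the change was made after data fixation, since SAP version 6.0 already carries that status. Leave the other factors as they are. If the bands are not adopted, use the label alone.

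Costs:

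- No new data and no choice of comparator age range.
- The SE of the log ratio rises by about 0.4% to 2% at 225 exposed women and 1.6% to 9% at 1,000.
- At 0.03% risk and 225 exposed, the banded ratio was undefined in 0.2% to 17% of simulated data sets, against 0% to 9% as planned.

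Banding does not cure one further problem. The pregnancy outcomes that Protocol 10.4.3 treats as serious adverse events cannot occur in non-pregnant comparators, so the serious-event ratio for pregnancy should carry a note saying so.

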Follow-up investigation should be conducted to obtain general information on the pregnancy. In addition, follow-up investigation of EDP outcome information is required for all EDP reports with an unknown pregnancy outcome. The pregnancy will be followed until completion or until pregnancy termination (eg, abortion induced) and the outcome should be reported to Pfizer. This information should be submitted as the follow-up investigation of the initial EDP report. In the case of a live birth, the absence of external malformations should be evaluated at birth. In the event of a termination, the reason(s) for termination should be specified and, if clinically possible, the structural integrity of the terminated fetus should be assessed by gross visual inspection (unless pre-procedure test findings are conclusive for a congenital anomaly and the findings are reported).

[figure not shown]
If the outcome of the pregnancy meets the criteria for a serious adverse event (ie, ectopic pregnancy, abortion spontaneous, foetal death in utero, death neonatal, or congenital anomaly [in a live born, a terminated fetus, an foetal death in utero, or a death neonatal]), the procedures for reporting serious adverse events should be followed.

Additional information on pregnancy outcomes that are reported as serious adverse events is as follows:

- Abortion spontaneous includes abortion and abortion missed.
- Death neonatal that occur within 1 month of birth should be reported as serious adverse events, without regard to causality. In addition, infant deaths after 1 month should be reported as serious adverse events when the investigator assesses the infant death as related or possibly related to exposure to the investigational product.

Additional information on exposure during pregnancy may be requested. Further follow-up of birth outcomes will be handled on a case-by-case basis (eg, follow-up on premature baby to identify developmental delays).

PFIZER CONFIDENTIAL

COMIRNATY Intramuscular Injection  
C4591006 NON-INTERVENTIONAL STUDY PROTOCOL  
Amended 5, 06 September 2022

---

In the case of paternal exposure, subjects will be provided with a document on "Disclosure of Information on Pregnant Partners," which is to be given to their partners. It must be documented that this document to be given to his partner has been provided to the subject.

Exposure during breast feeding

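### If the pregnancy subgroup is analysed, its risk ratio for any serious adverse event counts events that only pregnant women can have, so it is biased upward by construction; the size depends on rates the documents do not give.

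*SAP*

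**What the plan says.** SAP 5.4 lists "Pregnancy (women only) [absent, present"] among the factors for which "subgroup analyses of safety with respect to other factors indicated below will be performed, as necessary". SAP 9.2.3.4 then refers to every factor in 5.4 and states that "risk ratios between subgroups will be determined and graphically presented for the proportion of subjects with any serious adverse reactions". For factors other than sex and age it adds a Mantel-Haenszel ratio adjusted for sex and age (under 65, 65 and over). It closes with "Serious adverse events will also be analyzed in the same manner". SAP 9.1.3 attaches a 95% CI and a plot to each ratio. SAP 9.2.3.4 also plans a table by system organ class (SOC) and preferred term (PT) for Pregnancy, and allows a ratio to be omitted when a category has fewer than 5 subjects.

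On the event side, Protocol 10.4.3 names the pregnancy outcomes that meet the criteria for a serious adverse event: "ectopic pregnancy, abortion spontaneous, foetal death in utero, death neonatal, or congenital anomaly". For these, "the procedures for reporting serious adverse events should be followed". It adds: "Death neonatal that occur within 1 month of birth should be reported as serious adverse events, without regard to causality". On follow-up it says: "The pregnancy will be followed until completion or until pregnancy termination". Protocol 10.1 has all serious adverse events recorded in the CRF.

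Neither document removes these outcomes from the serious adverse event count by pregnancy, or tabulates them separately with pregnant subjects as the denominator.

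**The concern.** A risk ratio between two groups is interpretable when both can have the event being counted. Here they cannot. A miscarriage makes a pregnant woman a subject with a serious adverse event, and a non-pregnant woman has no counterpart. The ratio mixes two things: any difference in events both groups share (cardiac, thrombotic or COVID-19 events, say), and the mere existence of pregnancy outcomes in one group.

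Safety in pregnant or lactating women is listed as important missing information (Protocol 7.1, SAP 2.3.2), and the final analysis supports the re-examination application (SAP 3). A plotted ratio raised by its event definition could be read as a signal, and it could hide a real difference in shared events.

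**Working it through.** **1. Method check.** The plan states no expected rate, power or sample size for this comparison. Its only worked ratios are the mock rows in SAP Appendix 1. With RR = (a/n)/(b/m) and SE(log RR) = √(1/a − 1/n + 1/b − 1/m), the sex row (18/2220 versus 3/1099) gives RR = 2.97, SE = 0.6225 and 95% CI 0.88 to 10.06, as printed. The other eight rows that show a ratio also reproduce to two decimals, so this interval formula is used below.

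**2. Expected ratio when shared events are equally common.** Let p be the risk of a serious event that either group can have, equal in both. Let q be the risk of a recorded pregnancy-only serious event in the pregnant group, independent of the first. Then

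RR = [1 − (1 − p)(1 − q)] / p = 1 + q(1 − p)/p.

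This exceeds 1 whenever q > 0 and equals 2 when q = p/(1 − p), that is, when q is about equal to p. The documents give neither p nor q, so all values here are assumptions.

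| p \\ q | 0.5% | 1% | 5% | 10% | 15% |
|---|---|---|---|---|---|
| 0.5% | 1.995 | 2.99 | 10.95 | 20.90 | 30.85 |
| 1% | 1.495 | 1.99 | 5.95 | 10.90 | 15.85 |
| 2% | 1.245 | 1.49 | 3.45 | 5.90 | 8.35 |
| 5% | 1.095 | 1.19 | 1.95 | 2.90 | 3.85 |

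Example, p = 1% and q = 5%: 1 − 0.99 × 0.95 = 0.0595, and 0.0595/0.01 = 5.95.

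**3. Does the planned adjustment help?** The Mantel-Haenszel risk ratio is Σ(aᵢmᵢ/Tᵢ) / Σ(bᵢnᵢ/Tᵢ), where nᵢ and mᵢ are the pregnant and non-pregnant women in stratum i, aᵢ and bᵢ are those with an event, and Tᵢ = nᵢ + mᵢ. The comparison is among women only, so sex forms no strata. The stratum aged 65 and over will in practice hold no pregnant women. Its nᵢ and aᵢ are then 0, and it adds nothing to either sum. The adjusted ratio is simply the crude ratio in women under 65, with the same numerator problem.

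**4. Will the interval exclude 1?** That depends on the number of pregnancies, which is also not given. Illustrations with expected counts against 10,000 non-pregnant women (assumed):

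| Pregnant women (assumed) | p | q | RR | 95% CI |
|---|---|---|---|---|
| 100 | 1% | 5% | 5.95 | 2.66-13.29 |
| 100 | 5% | 5% | 1.95 | 1.07-3.56 |
| 100 | 1% | 1% | 1.99 | 0.50-7.98 |
| 50 | 5% | 5% | 1.95 | 0.84-4.55 |
| 30 | 2% | 5% | 3.45 | 0.92-12.94 |

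**5. After restriction.** Leaving pregnancy-only events out of the numerator sets q = 0, and the expected ratio is p/p = 1.00 for every p.

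**The case against.** A reader might infer that the ratio is bound to show a large excess. The documents do not support that. With no rates and no pregnancy count, the same formula gives 1.1 in one corner of the assumed range and about 31 in the other, and several illustrative intervals include 1. Only the direction is settled.

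Nor is every pregnancy outcome sure to be counted. SAP 2.1 starts safety evaluation after day 28 and ends it the day before any booster, so following a pregnancy to its end does not place its outcome in this analysis. Exposure during pregnancy as such is not recorded in the CRF (Protocol 10.1). Adverse events are defined as occurrences in a subject (Protocol 10.4.1, 10.4.2), and no text says whether an infant's death or anomaly counts as the mother's event. This lowers q but does not make it zero: ectopic pregnancy and spontaneous abortion are the woman's own events.

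The plan has partial safeguards. The analysis is conditional in SAP 5.4, very small categories may be dropped, the SOC/PT table and the listing of pregnant subjects would show miscarriages by name, and no hypothesis is tested (SAP 4). These reduce the risk of misreading. They do not correct the ratio, its interval or its plot. Nor does the SOC/PT table yield the shared-event ratio, since one woman may appear under several terms.

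Two extensions are tempting and should not be made. Ectopic pregnancy, miscarriage and foetal death do not plausibly inflate the ratio for Lactation, because those women would mostly be recorded as not lactating. And the serious adverse reaction ratio takes in pregnancy outcomes only where causality is not ruled out or is missing (Protocol 8.7.2, SAP 7). Removing them there would hide possibly vaccine-related outcomes in a population of interest.

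**Conclusion.** The point holds for the serious adverse event ratio by Pregnancy, if that analysis is produced. The ratio is biased upward by construction through at least ectopic pregnancy, spontaneous abortion and foetal death, and through neonatal death and congenital anomaly if these are attributed to the mother. The planned adjustment cannot remove the bias. With equal shared risk of 0.5-5% and pregnancy-only risk of 0.5-15%, all assumed, the expected ratio is about 1.1 to 31. It is at least 3.45 when q is 5% or more and p is 2% or less, and modest when q is small relative to p. Statistical exclusion of 1 cannot be predicted without the number of pregnancies. Both groups are vaccinated, so the ratio is in any case a descriptive comparison by recipient characteristic, not an estimate of a vaccine effect. This is a worthwhile, inexpensive improvement to one analysis; it does not undermine the study's main tabulations.

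**What to change.** In SAP 9.2.3.4, for the factor Pregnancy only:

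- Present the serious adverse event risk ratio, crude and adjusted, restricted to events that both groups can have. Define the exclusion by a listed set of pregnancy-, foetal- and neonatal-outcome PTs. Do not exclude whole SOCs, since that could drop events a non-pregnant woman can also have.
- Tabulate the excluded outcomes as n/N among pregnant subjects, with the exact 95% CI of SAP 9.1.3 and no ratio against non-pregnant women. State whether infant events are counted under the mother.
- Keep the all-event SOC/PT table. If an all-event ratio is still shown, label it as including events that only pregnant women can have.
- Leave the serious adverse reaction ratio as planned, with pregnancy outcomes identified beside it. Make no change for Lactation.

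The cost is SAP wording, a short term list and one flag on events already coded; no new data are needed. There are two drawbacks. The restricted ratio no longer covers every serious event, although the rest is shown next to it. And the SAP's revision history marks version 6.0 as written after all data were fixed, so the change must be labelled as added after data fixation.
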